6 STATISTICAL CONSIDERATION

6.1 Statistical Methods

Descriptive analyses will be used to assess demographic and medical history variables, camera usability, overall retinopathy, and participant satisfaction data. To assess usability of camera utilization, the proportion of inadequate images will be calculated. For participant satisfaction data, a response rate will be calculated followed by an overall mean score and standard deviation, and proportions for each of the six survey components. To assess overall retinopathy, a three-category outcome variable for retinopathy and referral at the individual level will be determined: (1) No retinopathy, (2) retinopathy without referral, and (3) retinopathy with referral. The following definitions will be determined (results for pairs of eyes will take into account that there may be some unreadable images): If the diagnosis in both eyes is no retinopathy then the individual has no retinopathy; otherwise, if either eye is considered severe, has proliferative diabetic retinopathy, clinically significant macular edema (CSME), or an inadequate image, the individual will be put into the retinopathy with referral category; likewise, if either eye is

mild/minimal or moderate retinopathy without CSME, then the individual will be placed into the retinopathy non-referral category.

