Study Objective(s)	
Primary To evaluate the usability of the FDA-approved RetinaVue Hand-Held 100 Camera in a population with multiple chronic conditions
 
Secondary
 
 • To evaluate pre-and-post-screening rates in the diabetic dialysis population. • To determine the proportion of overall retinopathy in a dialysis population • To evaluate participant satisfaction of screening utilizing the FDA-approved RetinaVue 100 hand-held camera
Study Design	This is a feasibility study.
Subject Population	Inclusion Criteria
key criteria for Inclusion and Exclusion:	
 • The subject must currently be seeking treatment for end-stage renal disease (ESRD) at one of the specified dialysis clinics. • The subject must be ≥ 18 years of age. 
Exclusion Criteria
 
 • The subject is <18 years of age.
Number Of Subjects	Up to 250 participants
Study Duration	
Each subject's participation may last up to 1 year.
 
The entire study is expected to last about 1 year.

Study Phases	(1) Screening for eligibility and obtaining consent, (2) Obtaining retinal images, completion of satisfaction survey, and medical record abstraction (3) For those participants recommended for referral, they will be given the opportunity to follow up with the remote provider.
Statistical And Analytic Plan	To assess usability of camera utilization, the primary objective, the proportion of inadequate images will be calculated.

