3.3 Study Population

Inclusion Criteria

- The subject must currently be seeking treatment for end-stage renal disease (ESRD) at one of the specified dialysis clinics.
- The subject must be ≥ 18 years of age.

Exclusion Criteria

- The subject is <18 years of age.

4 STUDY PROCEDURES (what will be done)

- Determine last documented retinal examination (electronic medical record)
- Determine cause of End-stage Renal Disease (ESRD) and vintage, I.e. how long patient has been on dialysis (paper chart)
- Determine patient demographics (electronic medical record)
 - DOS, DOB (age)
 - Gender, race
- Medical history (coronary artery disease, stroke, hypertension, if diabetes -duration)
- Medical labs (HbA1c, cholesterol, blood pressure)
- Smoking history
- Social determinants of health (education level, insurance status, etc).
- Check bilateral visual acuity with near card.
- Obtain bilateral retinal photographs with or without dilation.
- Complete the Usability survey.
- Complete the Participant Satisfaction survey.
- Upload patient images and metadata.
- Through the study PI, a board-certified ophthalmologist, interpret patient retinal images and return of diagnosis and management plan to dialysis unit including a wellness report to be given to individual subjects.
- Analyze data with biostatistician consultant
- Timeline. Quarter 1 (May –August 2016): Retinal image and metadata acquisition, clinic 1 and 2; Quarter 2 (September 2016-November 2016): retinal image and metadata acquisition clinic 3 and 4; Quarter 3 (December 2016-February 2017): data analysis; Quarter 4 (March 2017-May 2017): manuscript and presentation preparations.
- Subject results will be entered into the medical record. If something of note is found in a subject's

retinal scan, then staff at the dialysis clinic will provide follow up for any abnormalities found as part of clinical care.

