5 STUDY EVALUATIONS AND MEASUREMENTS

The following variables will be abstracted from medical records:

- Last documented retinal examination, cause of End-stage Renal Disease (ESRD) and vintage, I.e. how long patient has been on dialysis, DOS, DOB (age), gender, race, medical history (coronary artery disease, stroke, hypertension, if diabetes -duration), medical labs (HbA1c, cholesterol, blood pressure), smoking history, social determinants of health (education level, insurance status, etc).

Obtaining retinal images

- Nonmydriatic fundus images of both eyes were obtained from participants using the WelchAllyn RetinaVue™ 100 Imager. For those subjects with pupils smaller than 3 mm in either eye, a low dose dilation drop of 0.5% tropicamide will be administered to enlarge the pupil and assist in image capture. The images will be electronically sent via a HIPAA compliant portal to an offsite, board-certified ophthalmologist for remote interpretation. Following interpretation, a report will be generated that details any clinical findings and referral recommendations, which will then be distributed to individual subjects and uploaded to their electronic medical record. For those participants recommended for referral, they will be given the opportunity to follow up with the remote provider.

Participant satisfaction survey

- Participants will be asked to complete a brief participant satisfaction survey, which asks questions regarding their satisfaction with their exam experience. The survey utilizes a five-point Likert scale with responses ranging from strongly agree (1) to strongly disagree (5). The survey also allows for participants to provide qualitative observations about their experience. The survey asks about satisfaction of time to complete exam, comfort during the exam, comfort after the exam, first eye recovery after the camera flash, second eye recovery after the camera flash, and satisfaction with overall experience.

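### Section 6.1 derives referral from eye grade or an unreadable image and ignores the ophthalmologist's own recommendation, so the reported 'with referral' proportion need not equal the proportion recommended for referral.

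*Combined protocol and SAP*

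**What the plan says.** **Section 6.1 (Statistical Methods).** To assess overall retinopathy, "a three-category outcome variable for retinopathy and referral at the individual level will be determined": no retinopathy, retinopathy without referral, or retinopathy with referral. The assignment runs in order:

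- The first step reads: "If the diagnosis in both eyes is no retinopathy then the individual has no retinopathy".
- Next, a severe or proliferative grade, or macular edema that is clinically significant (CSME), places the participant in the referral category when one eye has it. An unreadable image does the same; the list of criteria ends with "or an inadequate image, the individual will be put into the retinopathy with referral category".
- The last step deals with lesser grades in one eye or both: "mild/minimal or moderate retinopathy without CSME, then the individual will be placed into the retinopathy non-referral category".

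The section notes that unreadable images will be taken into account. The second step is how it does so.

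**Section 5 (Study Evaluations and Measurements).** After remote interpretation, "a report will be generated that details any clinical findings and referral recommendations". The report goes to the participant and into the medical record. "For those participants recommended for referral, they will be given the opportunity to follow up with the remote provider"; the synopsis (Study Phases) says the same.

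**Section 4 (Study Procedures).** The ophthalmologist's diagnosis and management plan go back to the dialysis unit. Where the scan shows something of note, "staff at the dialysis clinic will provide follow up for any abnormalities found as part of clinical care".

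**The concern.** The study will hold two pieces of referral information on each participant: a category computed from grades, and a recommendation written by the ophthalmologist. Only the first is analysed, and its label gives no sign that it comes from a rule. Anyone reading a published 'with referral' proportion will probably take it as the share of screened dialysis patients whom the programme recommended for onward care. It is that share only if the ophthalmologist's recommendations follow the Section 6.1 rule exactly.

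At stake is how one secondary, descriptive result is read. Follow-up of those recommended for referral is the third study phase in the synopsis, so the number recommended is of practical interest. It is not the subject of any stated objective.

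**Working it through.** The plan gives no expected referral rate, so there is no figure to reproduce. The check is logical, followed by an illustration on assumed rates.

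**Step 1. Is the rule linked to the recommendation?** Section 6.1 names grades and image status and does not mention the report. Section 5 mentions the recommendation but gives no criteria for it. No section says that the ophthalmologist applies the Section 6.1 rule, or plans to tabulate the recommendation or compare it with the rule.

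**Step 2. Apply the rule to every pair of eyes.** Section 6.1 supplies seven eye states: none, mild/minimal, moderate, severe, proliferative, CSME and inadequate image. Two more were added as an assumption about what could be reported: a finding other than retinopathy, and a retinopathy outside the listed grades. Nine states give 9 × 10 / 2 = 45 unordered pairs:

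| Category under the rule | Pairs |
|---|---|
| With referral | 30 |
| Non-referral | 9 |
| No retinopathy | 3 |
| Unassigned | 3 |

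The total is 30 + 9 + 3 + 3 = 45. These are counts of combinations, not expected frequencies of patients.

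The rule can part from the recommendation in three ways:

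1. *Another finding, no retinopathy in either eye.* The participant falls in no retinopathy, which has no referral level. A referral for that finding cannot be recorded.
2. *Mild or moderate without CSME, nothing worse and no inadequate image.* The participant is always non-referral, even if the report recommends referral.
3. *One normal eye and one inadequate image, or two inadequate images.* The participant is always in retinopathy with referral, whatever the report says and although no retinopathy was graded.

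The third route is foreseeable, because the proportion of inadequate images is the plan's own usability measure. The 3 unassigned pairs all involve the assumed retinopathy outside the listed grades, either in both eyes or paired with an eye without retinopathy.

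**Step 3. How far apart could the two proportions be?** Let R be the rule-based proportion. Let u be the share of all participants whom the rule places in the referral category but the report does not refer. Let v be the share whom the report refers but the rule places elsewhere. Then

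proportion recommended = R − u + v, and discordant participants = (u + v) × N.

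N = 250 comes from Section 6.2. R = 20% (50 participants) and the range of 0 to 10% for u and v are assumed.

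| u | v | Recommended | Discordant |
|---|---|---|---|
| 0 | 0 | 20% (50) | 0 |
| 10% | 0 | 20 − 10 = 10% (25) | 25 |
| 0 | 10% | 20 + 10 = 30% (75) | 25 |
| 10% | 10% | 20 − 10 + 10 = 20% (50) | 50 |

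For comparison, the 95% sampling half-width at 20% is 1.96 × √(0.20 × 0.80 / 250) = 0.0496, about 5 points. A confidence interval would not reveal a gap of this kind. The last row shows that equal proportions can hide disagreement about individuals, which is why a cross-tabulation is needed and not only two percentages.

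**The case against.** The other side has a good deal in its favour.

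- *A fixed grade rule is a legitimate definition of referable disease.* This stands. Section 4 has images interpreted through the study's lead investigator, an ophthalmologist, so the rule may well be the working criterion. The documents do not say so. The recommendation has no stated criteria either, so it should not be treated as the truth against which the rule is judged.
- *Referral is not an objective, the analysis is descriptive and no data are lost.* This stands, and it limits the importance of the point. The recommendations are in the medical record and could be tabulated later, but as written the plan does not do so.
- *The follow-up wording in Sections 4 and 5 does not bear on the proportion.* This stands. Those passages do not enter the Section 6.1 variable.

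Three stronger readings are tempting and not supported. A reader might infer that the documents hold competing definitions of referral. Section 4 speaks of follow-up within clinical care and not of referral, and it can operate alongside the offer of the remote provider. A reader might also infer that someone with only an unreadable image gets no follow-up. Section 4 does not define what counts as being of note, and Section 5 does not limit the reasons for a recommendation, so the documents are silent. Finally, a reader might infer that participants without retinopathy are reported as not referred. That category makes no statement about referral.

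**Conclusion.** The point holds in a limited form. The 'with referral' proportion in Section 6.1 is a function of grade and image quality, and it need not equal the proportion recommended for referral in the reports. The three routes follow from the rule's wording. The first also assumes that the ophthalmologist can refer for findings other than retinopathy, which a report covering any clinical findings allows.

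No mismatch has been shown and its size is unknown. It is zero if the recommendations follow the rule exactly. The 10% to 30% range above only illustrates assumed inputs. A reader might infer a definite misclassification rate from it, but the documents supply nothing from which to estimate one. The effect is modest, and the change is still worth making because it is cheap and alters the referral figure that the study would report.

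**What to change.** In Section 6.1:

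1. Record the recommendation in each participant's report as a separate variable (yes/no), and report its proportion with the number of reports as denominator.
2. Cross-tabulate it with retinopathy status (none, present, ungradable) instead of nesting referral inside retinopathy. Ungradable could mean at least one inadequate image and no retinopathy graded in the other eye.
3. Keep the grade-based category, label it rule-based referable disease, and show its agreement with the recommendation in a two-by-two table with both discordant counts.

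Separately, the synopsis and Sections 4, 5 and 6.1 should be reconciled on how follow-up relates to the referral recommendation, including for participants with unreadable images. That choice belongs to the investigators.

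The cost is one column abstracted from existing reports, one extra table and some rewording. No study procedure changes.

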2 STUDY OBJECTIVE

Primary Objective:

- To evaluate the usability of the FDA-approved RetinaVue Hand-Held 100 Camera in a population with multiple chronic conditions

Secondary Objective

- To determine rates of overall retinopathy in a dialysis population
- To evaluate participant satisfaction of screening utilizing the FDA-approved RetinaVue 100 hand-held camera

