6.2 Sample Size and Power

The study aims to recruit and collect data from all individuals currently receiving treatment at the specified dialysis clinics. As such, the proposed sample (N=250) reflects the number of patients actively seeking treatment at those sites. Furthermore, this is a feasibility study and therefore 250 subjects is sufficient for the study team to determine the usability of the camera and to determine the prevalence of retinal disease in the dialysis population. In such a study, a power calculation is not indicated.

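### Section 6.1 counts participants with an inadequate image and no retinopathy seen as retinopathy cases, which biases the overall retinopathy proportion upward

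*Combined protocol and SAP*

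**What the plan says.** Estimating how common retinopathy is among dialysis patients is a secondary objective in the synopsis and in Section 2 ("To determine rates of overall retinopathy in a dialysis population"). Section 6.2 also says that 250 subjects are enough "to determine the prevalence of retinal disease in the dialysis population".

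Section 6.1 gives one variable for this purpose: "To assess overall retinopathy, a three-category outcome variable for retinopathy and referral at the individual level will be determined". The categories are (1) no retinopathy, (2) retinopathy without referral and (3) retinopathy with referral. Category 1 needs a negative diagnosis on both sides: "If the diagnosis in both eyes is no retinopathy then the individual has no retinopathy". Otherwise, if either eye has severe disease, proliferative diabetic retinopathy, clinically significant macular edema "or an inadequate image, the individual will be put into the retinopathy with referral category". Mild or moderate disease without macular edema goes to category 2.

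The definitions are introduced by a remark that "results for pairs of eyes will take into account that there may be some unreadable images". No handling of unreadable images is described other than the rule above. There is no category for participants who cannot be graded.

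**The concern.** Category 3 combines two different states: disease that was seen, and an image that could not be read. The second is a fact about the camera, the operator or the eye, and it is what the primary usability measure is meant to capture. Counting it as retinopathy carries camera failure into the disease estimate.

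At stake is a named secondary result. The analysis is descriptive, so no later step would correct the figure, and it could be cited as the prevalence of retinopathy in dialysis patients. The error is systematic, so recruiting more participants would not reduce it. The primary result, the proportion of inadequate images, is calculated separately and is not affected.

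**Working it through.** **Step 1: apply the rule to every pair of eye results.** With four possible results per eye there are 10 unordered pairs.

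| Pair of eyes | Category | Retinopathy seen? |
|---|---|---|
| none + none | 1 | no |
| none + mild/moderate | 2 | yes |
| mild/moderate + mild/moderate | 2 | yes |
| none + severe/proliferative/edema | 3 | yes |
| mild/moderate + severe/proliferative/edema | 3 | yes |
| severe/proliferative/edema in both | 3 | yes |
| mild/moderate + inadequate | 3 | yes |
| severe/proliferative/edema + inadequate | 3 | yes |
| **none + inadequate** | **3** | **no** |
| **inadequate + inadequate** | **3** | **no** |

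The last two pairs are labelled retinopathy with none seen.

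**Step 2: formula for the bias.** Take overall retinopathy as categories 2 + 3 over all imaged participants, and assume readable eyes are graded correctly. Every diseased participant then falls in category 2 or 3, unless an inadequate image hides the disease, in which case the person is in category 3 anyway. The excess consists of disease-free people with at least one inadequate eye:

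bias = (1 − p) × u0, with u0 = u / (1 − p + p × RR)

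Here p is the true prevalence, u the share of participants with at least one inadequate eye, u0 that share among disease-free people, and RR how many times more likely an inadequate eye is in diseased people. The bias cannot be negative.

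**Step 3: numbers.** The documents give no value for p, u or RR, so all three are assumptions and there is no stated figure to reproduce. The 250 is the maximum enrolment in Sections 3.2 and 6.2. At p = 30%:

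| RR | u = 5% | u = 10% | u = 20% |
|---|---|---|---|
| 1 | 3.5 points | 7.0 | 14.0 |
| 2 | 2.7 | 5.4 | 10.8 |
| 3 | 2.2 | 4.4 | 8.8 |

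Per 250 imaged, this is about 9, 18 or 35 people at RR = 1 and about 5, 11 or 22 at RR = 3.

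For scale, the 95% half-width is 1.96 × √(0.3 × 0.7 / 250) = 5.7 points. The bias passes it when u exceeds (0.0568 / 0.7) × (0.7 + 0.3 × RR), which is 8.1%, 10.5% or 13.0% for RR = 1, 2 or 3.

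**Step 4: other prevalences.** Same formulas, n = 250:

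| p | Half-width | Bias at u = 10%, RR 1 to 3 | u at which bias passes half-width, RR 1 to 3 |
|---|---|---|---|
| 20% | 5.0 points | 8.0 to 5.7 points | 6.2% to 8.7% |
| 30% | 5.7 | 7.0 to 4.4 | 8.1% to 13.0% |
| 50% | 6.2 | 5.0 to 2.5 | 12.4% to 24.8% |
| 60% | 6.1 | 4.0 to 1.8 | 15.2% to 33.4% |

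**Step 5: eye-level check of the remedy.** Assume p = 30%, a 15% inadequate rate per eye and a between-eye correlation of 0.5. Both eyes are inadequate in 0.15² + 0.5 × 0.15 × 0.85 = 0.086 of participants, and at least one in 0.30 − 0.086 = 0.214. With disease in both eyes:

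| RR | Section 6.1 rule | Ungradable counted absent | Ungradable dropped |
|---|---|---|---|
| 1 | 45.0% | 27.4% | 33.2% |
| 2 | 41.5% | 26.0% | 30.8% |
| 3 | 39.4% | 25.1% | 29.3% |

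The Section 6.1 rule equals the figure with every ungradable person counted as diseased, that is, the upper bound. The two bounds contain the true 30% in each row. Dropping ungradable people is not a safe substitute: with disease in one eye only it gives 31.7%, 28.3% and 26.2%, so its bias can go either way.

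**The case against.** The strongest objection is that no passage defines overall retinopathy as categories 2 + 3. The variable covers referral as well as disease, so the three categories might only be reported side by side. That is a fair limit on the claim about the overall proportion. Even so, categories 2 and 3 are both named as retinopathy, the variable is introduced for assessing overall retinopathy, and no other is offered. Reported separately, category 3 would still be inflated.

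The rule is also deliberate and visible, and the proportion of inadequate images will be reported. This helps only partly: that proportion counts images, not participants with no disease seen, so a reader cannot subtract it. Dilation of small pupils is planned "to enlarge the pupil and assist in image capture" and may lower the failure rate, but Section 6.1 still provides for unreadable images.

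The size depends heavily on assumptions. At a prevalence of 60% with RR = 3 and u = 10%, the bias is only 1.8 points. The half-width is a convenient yardstick, not a precision target in the plan; with 150 imaged it would be 7.3 points at p = 30%. Section 6.2 speaks of retinal disease, which is broader than the Section 6.1 variable, so the aim rests mainly on the synopsis and Section 2. All of this stands. It bears on the size and weight of the point, not on the misclassification.

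**Conclusion.** The concern holds: the rule is wrong as written. Two of the ten eye-result combinations are labelled retinopathy with none seen. The resulting error in overall retinopathy is upward or zero, provided readable eyes are graded correctly and the overall figure sums categories 2 and 3. It vanishes only if no disease-free participant has an inadequate eye.

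The size cannot be fixed from the documents. Over the assumed values at 30% prevalence it runs from 2.2 to 14.0 points. With 5% of participants affected it stays below the 5.7-point half-width; with 20% affected it exceeds it for all three values of RR. Higher prevalence makes it smaller and lower prevalence larger. It should be fixed, but it concerns a secondary, descriptive result in a feasibility study. The per-eye diagnoses allow correction at analysis.

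**What to change.** In Section 6.1, replace the three categories with four:

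1. No retinopathy: both eyes graded none.
2. Retinopathy seen in at least one readable eye, without referral.
3. Retinopathy seen in at least one readable eye, with referral.
4. Not gradable: no retinopathy seen and at least one eye inadequate.

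Report overall retinopathy over all imaged participants as two figures: (2 + 3) / all, and (2 + 3 + 4) / all. If readable eyes are graded correctly, the true proportion among those imaged lies between them. If a gradable-only estimate is added, state its denominator and that its bias can go in either direction.

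List referral for an inadequate image on its own line, and say whether that line overlaps category 3. A participant with mild or moderate disease in one eye and an inadequate image in the other has retinopathy seen; state which of categories 2 and 3 applies. If the referral test is meant to come before the non-referral test, say so. Neither clarification changes the overall proportion, and none of this alters clinical handling.

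The cost is a few sentences, one table row and one line. No new data are needed: Section 6.1 already works from a diagnosis for each eye, and under Section 5 "a report will be generated that details any clinical findings and referral recommendations". The drawback is that prevalence becomes a range as wide as the category 4 share. At p = 30% and RR = 1 that share lies between 0.7 × u and u: 3.5 to 5, 7 to 10 or 14 to 20 points at u = 5%, 10% or 20%.
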